5.4 Study Schedule/Study Visits

1. Remote Screening and Invitation to Participate (estimated time = 20 minutes)
2. Informed Consent and First Visit (estimated time = 3 hours)
3. Second Visit (estimated time = 3 hours)

Reminder text and/or telephone messages will be sent the day before and a phone call will be made the morning of the scheduled first and second visits.

During the 28-days study duration, the participants will receive daily phone calls or text, as reminders for the daily pill's intake. They also will be asked to fill out a weekly pill's intake report (Appendix 1) and send a picture of the filled report every 7 days to via e-mail or text message to the researcher contact.

Refer to Schedule of Activities (Appendix 1) and Study Schema (Appendix 1) for the detailed information.

Biospecimens:

40mL of blood will be collected by phlebotomy at the first and second visit. Plasma, peripheral blood mononuclear cells and serum will be separated either from EDTA, heparin or preservative free tubes. Roughly 300 microliters of whole blood will be taken out from the EDTA tubes, and used to measure Phosphatidylethanol (PEth). Peth is direct alcohol biomarker which is found in human blood following alcohol consumption.

Standard Operating Procedures (SOPs): Detailed guidance on study procedures can be found in specific SOPs. See the following documents in the appendix:

- SOP_Blood Processing_2023

Survey / Questionnaire Forms are in the appendix.

5.4.1 Screening and Recruitment

Participants will be recruited by word of mouth, printed advertising (flyers), social media. In the advertising, office phone number and project's email will be available for contact.

Once the individuals reach out (phone/email), they will answer the questionnaires (see in schedule of activities, appendix 1). Once the potential participant met the eligibility criteria, they will be scheduled for a in person visit at the research site, LSU Campus Multispecialty Clinic/Seton Building ([name]).

5.4.2 Informed Consent and Enrollment

After an invitation to participate in the research study is issued, potential research participants that are scheduled for a visit at the testing facility for formal informed consent followed by first visit schedule. All participants will be provided with information sheets in lay language and a complete verbal explanation regarding the reasons for conducting the study, the potential benefits of the information collected, and the risks involved. Health literacy sensitive consent and information documents will be used. Individuals not meeting basic literacy metrics will have the entire consent document read to them. Participants will be provided a copy of the informed consent and the consent process documented in study record.

5.4.3 Compensation

The participants will be paid as a compensation for their time and effort for their participation in this study.

The total amount of \$400 will be paid for each enrolled participant, the payment will be arranged as follows:

Day 0 (\$50): First visit, anthropometrics, vital signs and questionnaires.

Day 7 (\$75). Day 1 to day 7 of the diet intervention.

Day 14 (\$75): Day 8-14 of the diet intervention.

Day 21 (\$75): Day 15-21 of the diet intervention.

Day 28 (\$75): Day 22 to day 28 of the diet intervention.

Day 28 (\$50): Second visit, blood, anthropometrics, vital signs and questionnaires.

Each subject will receive a ClinCard in their first visit, and the credits will be released accordingly to the participation in the schedule above. The participants will be responsible for any taxes assessed on the compensation.

5.4.4 Monitoring plan for pills intake adherence

The participants will receive daily text messages as a reminder to take the pills and will be asked to confirm when the pills were already taken. Also, they will be given a weekly pill's intake report document (please, see on Appendix 1), and asked to send a picture of the filled document every 7 days. Finally, the participants will be asked to bring the tablets container back by the end of the study (Full test visit 2) and the pills left will be counted by the researcher¹⁴. The compliance to the intervention's schedule needs to reach 80% of the total 28 days, meaning that if the enrolled subject did not take the pills for more than 5 days they are going to be considered as drop out.

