2.3 Potential Risks

There are small, but real risks associated with some of the tests to be performed:

Interview & Completing Questionnaires: risks include emotional stress and fatigue.

Anthropometrics and Vital Sign: risk of fatigue, falls and device malfunction.

Phlebotomy: risk of discomfort and bruising. Some people may feel lightheaded or faint. There is also slight risk of infection.

Pills intake: risk of allergy, diarrhea or other gastrointestinal intolerance.

Unforeseen complications: there may be other complications that occur as a result of participation in this research study.

In order to minimize the potential risks, all the procedures will be performed by a trained professional, the materials and electronic devices to be used will be checked before the visits, sterile and single use materials for venipuncture, the participant's will be asked if they already consume vegetables from the Cruciferous vegetable's family (broccoli, arugula, bok choy, brussels sprouts, collard greens, cauliflower and cabbage).

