4.1.8 Exclusion Criteria

- Bowel-related diseases
- Diagnosed Diabetes

- Allergy or intolerance to broccoli.
- Any acute illness within the last 6 weeks.
- Chronic anti-inflammatory use or antibiotic treatment in the last 7 days.
- Acute illness withing the preceding six weeks (defined as fever, new antibiotic use or unscheduled healthcare visit – for illness).
- Acute alcohol intoxication upon arrival on the day of study visit.

Additional exclusion criteria:

- Any health issue that, the study investigator's judgement, confers excess risk for participation.

5. Study Methods

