5.2 Data Collection

We will use the REDCap (Research Electronic Data Capture) software toolset and workflow methodology designed for building and managing online surveys and databases to allow electronic data collection from multi-site clinical research studies. Data will be collected by interview and observer-assessments, and multiple levels of quality control will be used to ensure the highest level of data quality and security. The REDCap system allows for restricted access, read-and-write privileges for each database and data entry form. Routine data quality reports are produced evaluating range checks, valid fields, and missing fields. All changes to the database are logged and time stamped. In our prior work, the error rate was <1%. The participants will be randomized into placebo or BSE supplementation group, blood samples and data will be collected in two time-points, baseline day zero of treatment (Visit 1) and after 28 days of treatment (Visit 2). For the supplementation, the participants will be advised to take 2 capsules per day of the AVMACOL® (Nutramax Laboratories) supplement for a 28-days period. The placebo group will receive capsules with no BSE and will be instructed to take 2 capsules per day for the 28-days period.

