5.5.1 Sample Size Consideration

The sample size was calculated using the preliminary data for gut leak, the estimated number of participants was 13 (power= 0.8; alpha= 0.05; beta= 0.02). However, to increase the power in transitioning to humans, we plan to recruit 20 subjects for each group. In total, 40 participants will be recruited by convenience by printed advertising, post in social media and word of mouth.

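### Randomised participants who miss more than 5 of 28 pill days become drop-outs, and the plan defines no all-randomised analysis or missing-data method, so the iFABP comparison is open to bias in either direction

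*Combined protocol and SAP*

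**What the plan says.** Section 5.4.4 states that compliance "needs to reach 80% of the total 28 days" and that "if the enrolled subject did not take the pills for more than 5 days they are going to be considered as drop out". Adherence is tracked by daily text confirmations, weekly reports and, at the second visit, a count in which "the pills left will be counted by the researcher". The section does not say which source decides.

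Section 5.2 places blood sampling at day 0 and after 28 days. The primary outcome is iFABP concentration (section 4.1.3), and section 5.5 compares group changes by t-test or Wilcoxon-Mann-Whitney, with adjustment for sex, age, BMI, race/ethnicity and substance use. Section 5.5.2, headed as the planned analysis, contains no analysis method. No section names an intention-to-treat or per-protocol set, says whether drop-outs' Visit 2 samples are used, or gives a missing-data method.

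Section 5.5.1 calculates 13 participants, without saying whether per group or in total, and then states "we plan to recruit 20 subjects for each group". It attributes the increase to power and gives no allowance for attrition. Section 2.3 lists "Pills intake: risk of allergy, diarrhea or other gastrointestinal intolerance".

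**The concern.** Randomisation protects the comparison only while everyone randomised stays in it. A rule that acts on behaviour after randomisation can remove different kinds of people from the two arms, and baseline balance then no longer guarantees a fair contrast.

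The risk is specific in this trial. Section 2.1 describes iFABP as a biomarker of epithelial injury, and section 2.3 gives gut intolerance as a reason someone might stop the pills. The reason for leaving may therefore be tied to the primary outcome. The covariates in section 5.5 do not include gut tolerance, so the planned adjustment would not remove this selection. A positive result could then not be separated from selection of the people who tolerated the pills.

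**Working it through.** **1. Is the rule consistent with itself?** 80% of 28 days is 0.80 × 28 = 22.4 days. Five missed days leave 23/28 = 82.1% (kept); six leave 22/28 = 78.6% (drop-out). The two halves of the rule agree, so the problem is what follows from the rule, not its threshold.

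**2. Size of the possible bias.** The documents give no non-adherence rates and no link between non-adherence and iFABP, so the inputs here are assumptions. Set the iFABP change to SD 1 with no true effect. Let a latent tendency to stop pills have correlation r with a worse change, and exclude the worst fraction p of each arm. With φ the standard normal density and c the (1 − p) normal quantile, the mean change among those kept is −r × h(p), where h(p) = φ(c)/(1 − p).

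| p | c | φ(c) | h(p) |
|---|---|---|---|
| 5% | 1.645 | 0.1031 | 0.1086 |
| 10% | 1.282 | 0.1755 | 0.1950 |
| 15% | 1.036 | 0.2332 | 0.2743 |
| 25% | 0.674 | 0.3178 | 0.4237 |

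The bias (BSE minus placebo) is −r × [h(p on BSE) − h(p on placebo)]; negative favours BSE.

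| Excluded, BSE vs placebo | Difference in h | Bias, r = 0.5 | Bias, r = 0.7 |
|---|---|---|---|
| 15% vs 10% | 0.0793 | −0.04 SD | −0.06 SD |
| 15% vs 5% | 0.1657 | −0.08 SD | −0.12 SD |
| 25% vs 5% | 0.3151 | −0.16 SD | −0.22 SD |
| 5% vs 25% | −0.3151 | +0.16 SD | +0.22 SD |
| Equal, same mechanism | 0 | 0 | 0 |

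Simulation of 40,000 null trials per setting (20 per arm, two-sided t-test at 5%) reproduces these biases. Rejection rates for r = 0.5 and 0.7 are 5.3% and 5.5% at 15% vs 10%, 5.9% and 6.4% at 15% vs 5%, and 7.4% and 10.3% at 25% vs 5%. With equal 20% exclusion the rate stays at 5.0%.

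Bias can also arise at equal rates if the mechanism differs by arm: with 20% excluded in both arms and r = 0.5 on BSE only, a simulation of the same size gives −0.17 SD.

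**3. Loss of sample.** The 13 in section 5.5.1 cannot be reproduced because no effect size or SD is given. Read as 13 per group with a two-sided 5% t-test and 80% power, it implies a standardised effect of 1.145. At that effect:

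| Evaluable per arm | Power |
|---|---|
| 20 | 94.2% |
| 16 | 88.0% |
| 13 | 80.0% |
| 12 | 76.5% |

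On that reading up to 20 − 13 = 7 losses per arm leave the nominal 80%. Without it, the effect detectable with 80% power rises from 0.91 SD at 20 per arm to 1.02 SD at 16.

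**The case against.** **Exclusion is not written.** Section 5.4.4 says drop-out, not removal from the analysis, and the pill count itself takes place at Visit 2. This stands: exclusion is an inference. It is the natural one, because the outcome is a two-visit change and no other handling is given. If the sponsor means something else, the primary analysis population is undefined and the same amendment is needed.

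**Bias toward BSE is not established.** A reader might infer that the rule favours BSE. The documents do not support that. Section 2.3 lists intolerance for pill intake without separating active from placebo. Section 4.1.8 excludes broccoli allergy or intolerance and bowel-related disease, which should reduce differential stopping. Reminders, weekly reports and weekly payments support adherence in both arms. No section gives a figure that would justify 25% versus 5%, and a modest imbalance leaves the error rate near 5%.

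**Sample loss has a margin.** Recruiting 20 against a calculated 13 absorbs considerable loss if 13 is per group. That stands, subject to the unstated unit.

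**Two further inferences go beyond the text.** The exclusion "Acute alcohol intoxication upon arrival on the day of study visit" might be read as removing randomised participants at Visit 2, but it sits among eligibility conditions and refers to a single visit, so that use is conjecture. Someone taking one capsule a day (28 of 56, or 50%) might be thought to pass the day rule. But section 5.2 says "the participants will be advised to take 2 capsules per day", so a one-capsule day can equally be read as a day on which the pills were not taken, and the count would show the leftover capsules.

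**Conclusion.** The concern holds in limited form. The plan contains a post-randomisation, adherence-based reclassification with nothing to offset it, and followed on its natural reading it gives an adherers-only comparison for the primary outcome. That loss of the randomised comparison does not depend on any assumed rate.

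The size and direction of bias do depend on assumptions. When the same selection mechanism acts in both arms, bias requires exclusion rates that differ by arm and are related to the iFABP change. Over the unequal scenarios shown, it runs from 0.04 to 0.22 SD in either direction. The upper end rests on a large assumed imbalance and should not be read as an expected value. Reduced power is a lesser issue.

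The point should be settled before analysis because it decides who enters the primary comparison.

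**What to change.** Replace the drop-out sentence in section 5.4.4, and carry the analysis sets into section 5.5, with wording such as:

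> Participants are asked to attend Visit 2 and give blood whatever their adherence, unless they withdraw consent. The primary analysis includes all randomised participants in their assigned group, with a stated method for missing Visit 2 values. Participants who took at least 80% of assigned capsules (at least 45 of 56 taken, judged from the count of capsules left) form a secondary per-protocol set.

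The count follows from 2 × 28 = 56 and 0.80 × 56 = 44.8, rounded up to 45. If exactly 56 capsules are dispensed, this means at most 56 − 45 = 11 left; the number dispensed is not stated and should be. The missing-data method is needed because section 6.1 allows withdrawal at any time, so some Visit 2 values may be absent. The sponsor should also clarify whether the intoxication criterion in section 4.1.8 applies only at enrolment.

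The cost is a short amendment with IRB approval. Visit 2 blood, its payment and the pill count are already planned. The downside is that non-adherence dilutes the all-randomised estimate; the per-protocol set still shows the result among adherers.

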5.5 Statistical Method

The data obtained will be analyzed using R and SAS software. After performing normality tests, we will compare group changes in each biomarker according to the most appropriate statistical test: either t-test (normal distribution) or Wilcoxon-Mann-Whitney (non-normal distribution). Multivariate methods will be applied to verify the relationship between BSE supplementation and gut leak, BSE supplementation and inflammation and BSE supplementation and oxidative stress. The data will be adjusted for following confounders: sex, age, BMI, race/ethnicity and substance use.

Scientific Rigor: The principal investigator (PI) will be blinded for the randomization; the pill bottles will be labeled as "Tablets A" or "Tablets B" by the manufacturer. The PI will be responsible for the data collection's quality control, as well as the experiments execution, assuring proper negative and positive controls and appropriate replicates within experiments. All the findings of the present research will be analyzed and reported with full transparency. The product's manufacturer will not have any authority over the study design, results or scientific publication.

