4.1.3 Primary Outcome Variable

iFABP concentration.

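### The between-arm comparison is of changes from baseline, and the adjustment list omits each biomarker's own day-0 value, which costs precision but does not bias the result.

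*Combined protocol and SAP*

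**What the plan says.** The primary outcome in section 4.1.3 is "iFABP concentration"; section 4.1.4 names IL-6 and total antioxidant capacity as secondary. Under section 5.2, blood is taken from participants at Visit 1 (day 0) and at Visit 2 after 28 days, so each biomarker has a baseline and a follow-up value.

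Section 5.5 describes two layers of analysis:

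- An unadjusted comparison: "we will compare group changes in each biomarker". The choice is between a t-test and a Wilcoxon-Mann-Whitney test, made after normality tests. Neither test takes a covariate.
- An adjusted analysis: "Multivariate methods will be applied to verify the relationship between BSE supplementation and gut leak", and likewise for inflammation and oxidative stress. The covariates are given in one sentence: "The data will be adjusted for following confounders: sex, age, BMI, race/ethnicity and substance use".

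The baseline biomarker is not on that list, and no other section adds it. Section 5.5.2, despite its title, contains no analysis method. The plan does not say whether change is absolute, percentage or on a log scale, whether the adjusted model's outcome is the change or the day-28 value, or which of the two layers is primary.

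**The concern.** Subtracting baseline from follow-up fixes the slope on baseline at 1. When the two measurements are imperfectly correlated, the best-fitting slope is smaller (it equals rho when variances are equal), and the change score carries extra baseline noise into the treatment estimate. Regression on baseline estimates the slope and removes that noise.

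Section 5.5.1 raised recruitment to 20 per group in order to gain power. Baseline adjustment would add power from samples already drawn, and the plan as written does not use it. At stake are the width of the confidence interval for iFABP and the chance of detecting an effect in 40 people.

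**Working it through.** **The plan's own figure.** Section 5.5.1 says "the estimated number of participants was 13", with power 0.8 and alpha 0.05. It gives no effect size, SD, sidedness or per-group/total label, so the figure cannot be reproduced. It can only be inverted: if 13 is per group and the test is a two-sided t-test, it implies a standardised effect of about 1.15. Nothing in it supplies a correlation between visits, so the calculation below needs assumed values.

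**Inputs.** From the documents: 20 per arm, N = 40, two measurements per biomarker. Assumed: common variance s² at both visits, a linear relation, complete data, and rho (the within-arm correlation of baseline with day 28) of 0.3, 0.5, 0.7 or 0.9.

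**Variance per participant.**

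- Change score: 2s²(1 − rho)
- ANCOVA: s²(1 − rho²) = s²(1 − rho)(1 + rho)
- Ratio, ANCOVA to change: (1 + rho)/2

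Estimating the slope inflates the ANCOVA variance by 1 + 1/(N − 4) = 1 + 1/36 = 1.028. The equivalent n is 20 divided by the resulting ratio.

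| rho | (1+rho)/2 | × 1.028 | Simulated ratio (20,000 trials) | Change-score n per arm matching 20 by ANCOVA |
|---|---|---|---|---|
| 0.3 | 0.65 | 0.67 | 0.665 | 29.9 |
| 0.5 | 0.75 | 0.77 | 0.777 | 25.9 |
| 0.7 | 0.85 | 0.87 | 0.877 | 22.9 |
| 0.9 | 0.95 | 0.98 | 0.974 | 20.5 |

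The break-even point at N = 40 is (1 + rho)/2 = 36/37, or rho of about 0.95. Above it the estimated slope costs slightly more than it returns.

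**Power illustration.** CV 0.6 and a 35% reduction are further assumptions, not figures from the plan. On the log scale the SD is √ln(1 + 0.6²) = √ln 1.36 = 0.555, and the effect is −ln 0.65 = 0.431. At rho 0.5:

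- Change-score SD is 0.555 × √(2 × 0.5) = 0.555, so the standardised effect is 0.431/0.555 = 0.78.
- ANCOVA SD is 0.555 × √(0.75 × 1.028) = 0.487, so the standardised effect is 0.431/0.487 = 0.885.

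With 20 per arm, two-sided alpha 0.05, and 38 or 37 error degrees of freedom, noncentral-t power is:

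| rho | Change score | ANCOVA | Gain (points) |
|---|---|---|---|
| 0.3 | 53% | 70% | 17 |
| 0.5 | 67% | 78% | 11 |
| 0.7 | 87% | 91% | 4 |

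**Chance baseline imbalance.** The correlation between the change-score estimate and the chance difference in baseline means is −√((1 − rho)/2): −0.59, −0.50 and −0.39 at rho 0.3, 0.5 and 0.7. Its square, (1 − rho)/2, is exactly 1 minus the variance ratio (1 + rho)/2. Sensitivity to the baseline draw is therefore the same loss seen from another side, and must not be counted again.

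**The adjusted model.** If its outcome is the change, adding baseline gives the same treatment estimate as ANCOVA on the day-28 value. If its outcome is the day-28 value, leaving baseline out discards the baseline information altogether. Adding baseline resolves both cases.

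**The case against.** A comparison of changes is a valid test in a randomised trial, this is a 40-person pilot, and the size of the loss rests wholly on assumed inputs. All of that stands. If iFABP is very stable within a person, with rho near 0.9, there is almost nothing to gain.

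One might add that the unspecified multivariate methods could include baseline. The plan names its covariates, however, and baseline is not among them. Nor does pilot status remove the point: the protocol sets out to test a hypothesis, gives a power calculation and enlarges the sample for power.

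A reader might also infer more than the documents support:

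- *That chance imbalance and regression to the mean bias the result.* Under randomisation they do not; they add variance, which the ratio already counts.
- *That the plan analyses raw, absolute differences.* It never states the scale of the change.
- *That the whole analysis is on change scores.* This is certain only for the unadjusted test; the outcome of the adjusted model is not stated.
- *That a sizeable loss is certain.* It depends on rho, which is not given.
- *That every biomarker should be log-transformed.* Nothing in the documents shows this, for example for total antioxidant capacity.

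**Conclusion.** The point holds as a loss of precision. The omission and its direction are clear from the text and the algebra; its size is conditional. The variance of the treatment estimate would fall by about 33%, 23%, 13% and 2% at rho 0.3, 0.5, 0.7 and 0.9, assuming equal variances, a linear relation and 40 complete participants. These figures concern the t-test branch; the Wilcoxon-Mann-Whitney branch was not calculated, although that test also takes no covariate. The power gains of 17, 11 and 4 points rest in addition on an assumed CV and effect. The planned comparison remains valid, so this is an improvement that should be made because it is nearly free, not a flaw that undermines the trial.

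**What to change.** Amend section 5.5, before unblinding, as follows:

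- Primary analysis: linear regression of day-28 iFABP on arm and baseline iFABP, with the scale prespecified. If iFABP is expected to be skewed, use logs of both values and report the geometric mean ratio with its 95% CI.
- IL-6 and total antioxidant capacity: the same form, each with its own baseline and a scale prespecified for that biomarker.
- Adjusted model: state its outcome, and add the baseline biomarker to the five covariates already listed.
- Keep the change-score test as a supportive analysis.

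The cost is a few sentences and one degree of freedom per model. No extra samples, visits or participants are needed.

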4.1.4 Secondary Outcome Variables

IL-6 and total antioxidant capacity.

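### A normality test picks the iFABP effect measure, the comparison of change leaves out baseline, and no analysis is named primary; one prespecified baseline-adjusted model would settle all three

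*Combined protocol and SAP*

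**What the plan says.** Section 5.5 (Statistical Method) sets a two-stage rule: "After performing normality tests, we will compare group changes in each biomarker", and the comparison is then made "according to the most appropriate statistical test: either t-test (normal distribution) or Wilcoxon-Mann-Whitney (non-normal distribution". It does not name the normality test, its level, or what it is applied to (each arm, pooled data or residuals). It states no scale for the change and plans no transformation.

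The same section adds a second analysis: "Multivariate methods will be applied to verify the relationship between BSE supplementation and gut leak", and likewise for inflammation and oxidative stress. It continues: "The data will be adjusted for following confounders: sex, age, BMI, race/ethnicity and substance use". The baseline biomarker is not in that list, although section 5.2 has blood drawn at day 0 and day 28. No model is named, and nothing says which of the two analyses carries the primary conclusion.

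The primary outcome in 4.1.3 is "iFABP concentration" and the secondary outcomes in 4.1.4 are "IL-6 and total antioxidant capacity", with no scale or summary measure. Section 5.5.2, headed Planned Analysis, describes no analysis.

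**The concern.** A t-test on change estimates a difference in mean change. Wilcoxon-Mann-Whitney compares the rank ordering of change. Under the rule, the observed data choose which of these answers the primary question, and the choice is made again for each marker. iFABP, IL-6 and total antioxidant capacity could be reported on different effect measures, none of them fixed in advance.

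Two further gaps sit beside this. Analysing change instead of adjusting for baseline wastes precision in a trial of 40 people. And with a two-group test and an adjusted analysis of unstated rank, the primary result could be taken from either after the data are seen.

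**Working it through.** **The plan's own figure.** Section 5.5.1 gives a calculated size of 13 with "power= 0.8; alpha= 0.05; beta= 0.02". It gives no effect size or SD, so 13 can be neither reproduced nor refuted. Working backwards (two-sided 0.05, power 0.80, normal approximation), 13 per arm implies d = (1.960 + 0.842) × √(2/13) = 1.10. If 13 is the total, d = 2.802 × √(2/6.5) = 1.55. Power 0.8 means beta 0.20, so the stated beta needs correcting as a separate matter. Nothing here fixes a distribution for iFABP, so the rest is illustration.

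**Inputs.** From the documents: 20 per arm, alpha 0.05, day 0 and day 28. Assumed: two-sided testing, lognormal marker, CV 0.6, baseline to day-28 correlation ρ = 0.5 on the log scale, 35% reduction, Shapiro-Wilk in each arm at 5%, change on the untransformed scale.

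**Closed form on the log scale.**
- Log SD: s = √ln(1 + 0.6²) = 0.5545. Effect: ln 0.65 = −0.431.
- Log change: SD = s√(2(1 − ρ)) = 0.5545; SE = 0.5545 × √(2/20) = 0.175; effect/SE = 2.46; t-based power (38 df) 67%.
- ANCOVA: SD = s√(1 − ρ²) = 0.480; SE = 0.152; effect/SE = 2.84; t-based power (37 df) 79%.
- Variance ratio, ANCOVA to change: (1 + ρ)/2 = 0.75 here, 0.70 at ρ = 0.4 and 0.90 at ρ = 0.8.

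**Simulation, same inputs.**

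| Analysis | Power |
|---|---|
| Planned rule, untransformed change | 51% |
| Always t-test, untransformed change | 48% |
| Always Wilcoxon, untransformed change | 51% |
| t-test, log change | 66% |
| ANCOVA, raw scale | 70% |
| ANCOVA, log scale | 79% |

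The rule performs like the better fixed test on the same scale, so the pre-test is not where power is lost. Baseline adjustment is worth 70 − 51 = 19 points on the raw scale, or 79 − 66 = 13 on the log scale. Logging is worth 66 − 51 = 15 points on change, or 79 − 70 = 9 with ANCOVA. At CV 0.9 the rule has 31%, a t-test on log change 40% and log ANCOVA 51%.

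**Wider range** (3,000 trials per setting; log SD 0.3 to 0.8; ρ 0.4 to 0.8; effect set so that log ANCOVA has about 80%):
- Rule 46% to 69%; raw ANCOVA 60% to 79%; log ANCOVA 79% to 80%.
- Raw ANCOVA gains 3 points (57.3% to 60.4%, log SD 0.8, ρ = 0.8) to 22.5 points (51.1% to 73.6%, log SD 0.5, ρ = 0.4) over the rule. The gain shrinks as ρ rises.
- Log ANCOVA gains a further 2 points (78.7% to 80.4%, log SD 0.3, ρ = 0.4) to 19 points (60.4% to 79.0%, log SD 0.8, ρ = 0.8). This gain grows with skew.
- The pre-test chose the t-test in 77% to 79% of trials at log SD 0.3, 51% to 55% at 0.5 and 16% to 20% at 0.8. In mid-range, chance largely settles the effect measure.
- Null rejection by the rule was 4.6% to 5.3% (6,000 trials per setting).

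**Counter-case, marker normal on the raw scale, ρ = 0.6, CV 0.15, 0.25, 0.35.** Rule 71% to 72%; raw ANCOVA 79% to 80%; log ANCOVA 78%, 77%, 70%. Baseline adjustment on the raw scale still gains 8 to 9 points, but at CV 0.35 log ANCOVA falls slightly below the rule.

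**The case against.** Several stronger readings are tempting, and the case against them is good.

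- A reader might infer that the pre-test inflates type I error or itself costs power. Neither shows in the simulations: null rejection stays near 5%, and the rule matches the better fixed test on the same scale. Deleting the pre-test alone would fix the effect measure and recover almost no power.
- A reader might infer that the plan specifies raw change. It does not; it speaks of changes with no scale. If change were taken on the log scale, the rule would equal a fixed t-test (66% each in the illustration), leaving only the baseline-adjustment gap. Untransformed change is the natural reading where no transformation is planned, but it is an inference.
- A reader might infer that log analysis is always better. The documents give no distribution, SD or correlation for any marker, and the counter-case shows that logging can cost power.
- A reader might see a contradiction between Wilcoxon-Mann-Whitney, which gives no adjusted estimate, and the promise to adjust. The adjustment sentence follows the multivariate step and can belong to it, so the text is not contradictory. What is missing is the rank of the two analyses.

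This is also a pilot, and other choices, such as raw-scale ANCOVA or one fixed rank test, would define the effect measure too. All of that stands. It does not touch the core: the effect measure is chosen by the data, the baseline value is unused as a covariate, and the primary analysis is unnamed.

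**Conclusion.** The point holds in this limited form. Under any distribution, section 5.5 leaves the iFABP effect measure to a normality test and does not say which analysis is primary. That is a matter of definition and interpretability; the tests themselves remain valid.

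The power cost depends on assumptions. Leaving out baseline costs about 19 points in the main illustration (51% against 70%), 3 to 22.5 points across the lognormal settings, and 8 to 9 points if the marker is normal on the raw scale with ρ = 0.6. A further gain from the log scale (70% to 79% in the illustration) arises only if values are right-skewed. All these figures take the planned change to be untransformed. The change should be made because it costs little and the trial is small; the plan as written would not produce an invalid test.

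**What to change.** In section 5.5:

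1. Delete the normality pre-test.
2. Name as primary one linear model (ANCOVA) of day-28 iFABP on treatment group and baseline iFABP, and report the adjusted group difference (a ratio of geometric means if logged) with its confidence interval. State whether the test is one- or two-sided.
3. Use the same model for IL-6 and total antioxidant capacity.
4. Fix the scale for each marker before unblinding: log for right-skewed concentrations, justified from the preliminary data or from blinded baseline values.
5. Keep Wilcoxon-Mann-Whitney on change as a fixed sensitivity analysis, reported whatever the data look like.
6. State the form of the multivariate analysis and its supportive role, and say where the listed covariates enter.

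The cost is plan wording and its review; no visit, sample or assay is added. There are two downsides. Logging needs a fixed rule for values below the assay limit. And if a marker proves near normal on the raw scale, logging can lose some power (log ANCOVA 70% against raw ANCOVA 80% at CV 0.35 in the counter-case), which is why the scale should be justified and not assumed.
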